All subjects who are randomized to Caplyta will receive 42mg/day starting the first week of the study. Subjects will be seen every two weeks for 8 weeks. Dosage changes and reductions will not be permitted. After study conclusion (week 8), the dose will be discontinued.

Randomization

Participants are randomized (1:1) to receive placebo or Caplyta by the investigational pharmacy at the University of Chicago. The study blind will be maintained by making placebo and active treatments appear identical in size, weight, shape, and color. Dosage changes and reductions will not be permitted during the study and participants will be discontinued if they experienced intolerance.

Blinding

Blinding is critical to the integrity of this clinical study. However, in the event of a medical emergency or pregnancy in an individual subject, in which knowledge of the investigational product is critical to the subject's management, the blind for that participant may be broken by the treating physician.

Treatment Duration, Visit Frequency, and Procedures

This is an 8-week study (8 weeks of acute treatment). Subjects will be seen at baseline and then every two weeks after that for a total of 5 visits.

Diagnostic Evaluation

Psychiatric evaluation will use the MINI International Neuropsychiatric Interview with a module for BPD.

Assessments at Each Visit

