Data collected will consist of demographic data, subjective (self-report questionnaires, interview responses, ratings), physiological (heart rate and blood pressure), and cognitive (e.g., neurocognitive tasks). Access to individually identifiable private information about human subjects will be limited to Drs. [name] and [name] and their staff and will be collected specifically for the proposed research project. All collected data will be stored utilizing a 4-digit subject identification code, linked to separately stored identifying information via a coded log only available to the PIs.

Prior to inferential analyses, descriptive statistics, including distributions, means, standard deviations, skewness, and kurtosis will be generated. Data will also be examined for the pattern and mechanism of missing data. Continuous data will be tested for normality and homogeneity of variance. The integrity of the randomization will be evaluated using t-tests for continuous variables and chi-square tests for categorical variables. Further, baseline differences between those who enter the study and those who drop out before treatment will be evaluated. Subsequent outcome analyses will be adjusted for baseline differences using covariance procedures.

All enrolled subjects will be included in the analyses of baseline demographics and safety according to an intent-to-treat (ITT) principle. For statistical analysis, the full-analysis set will be defined as all participants who took at least 1 dose of the study drug and had at least 1 post-baseline primary efficacy assessment. The safety-analysis set will be defined as all randomized participants who took at least 1 dose of the study drug and completed at least 1 follow-up safety assessment.

The statistical model will be a linear mixed-effects regression model (LME) that includes terms for treatment group, time, and treatment-by-time interaction. The analyses will run using the nlme package on R for Windows (R Foundation, Vienna, Austria; <http://www.r-project.org>). Literature suggests LME without imputation may provide more accurate and stable results than LME models using fixed and multiple imputation methods for handling missing data, so no imputation will be undertaken for missing data. All tests of hypotheses will be performed using a two-sided significance level of 0.05.

Sample Size

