The sample size was calculated for the primary endpoint of change from baseline. Assuming a similar magnitude of effect seen in other studies of medications for BPD, it was determined that 25 participants would be needed in each treatment group to detect a difference with an overall 5% type-I error risk. Given the particularly low rates of adverse events reported with Caplyta, as well as its more positive side effect profile in terms of weight gain, we expect few drop-outs from the study and therefore a smaller sample is needed (60 total).

Data Handling and Record Keeping

All subject data will be maintained by the study personnel under the supervision of the principal investigator. Subjects will be seen at the University of Chicago. Patient binders will be kept in a locked room only accessible to research staff.

Data and Safety Monitoring Plan

1. Responsibility for Data and Safety Monitoring

The PI will have overall responsibility for monitoring the integrity of study data and participant safety.

2. Procedures for Monitoring Participant Safety

The PI will implement the following procedures to ensure data integrity and the safety of participants during the study.

- A number of elements of the research plan are intended to minimize the risks of study participation. If subjects become actively suicidal with intent and plan to kill themselves, the PI will evaluate them and refer them for immediate non-study treatment. Any participant endorsing suicidal thoughts with intent and plan will be immediately evaluated by the PI and referred to a higher level of care if clinically indicated.
- The PI will evaluate patient safety and resolve any safety issues if necessary, as such issues arise. The PI will also be responsible for preparing written summary reports of adverse events and will prepare a written report summarizing any decisions that are made pertaining to participant disposition.
- Data integrity and confidentiality will be safeguarded as stated above in the Data Handling and Record Keeping Section.

3. Reporting Adverse Events

- Any serious adverse event will be reported to the Institutional Review Board (IRB) at the University of Chicago in a full written report within 10 working days of the event. For fatal/life-threatening serious adverse events, the PI will notify the IRB Chair by phone immediately.

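### The primary model's covariates are left to whatever baseline differences appear, and adjustment for the baseline Zanarini score is not prespecified

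*Combined protocol and SAP*

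**What the plan says.** The relevant text is in the Data Analysis section. It first plans significance tests of baseline variables between arms: "The integrity of the randomization will be evaluated using t-tests for continuous variables and chi-square tests for categorical variables". It then plans a baseline comparison of people who enter with people who drop out before treatment. The next sentence is the adjustment rule: "Subsequent outcome analyses will be adjusted for baseline differences using covariance procedures". No variable list, threshold or selection rule is given for either comparison.

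The same section describes the model: "The statistical model will be a linear mixed-effects regression model (LME) that includes terms for treatment group, time, and treatment-by-time interaction". Baseline Zanarini score is not among the terms. The section says that all visits will be used, but not whether the baseline visit is a response value or which model term is the primary test. The Efficacy evaluation section defines the primary outcome as change from baseline on the Zanarini scale. That score is also an inclusion criterion (at least 9), so every eligible participant has one.

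**The concern.** When allocation is random, baseline differences between arms are chance. Testing them therefore says little about whether randomization worked. If the result also decides which covariates enter the outcome model, chance picks the model after the data have been seen. The plan collects many baseline measures (depression, anxiety, disability, quality of life, impulsivity and compulsivity scales, laboratory values, cognitive tasks), so there are many candidates.

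The variable with the strongest claim to be in the model is the baseline value of the outcome itself. Under a test-triggered rule it would enter only when it happened to differ between arms, which at a 0.05 threshold is about one trial in twenty. With 60 participants, both a primary model that is not fixed and a loss of precision matter.

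**Working it through.** **Inputs from the documents.** Two-sided 0.05; 1:1 allocation; 60 in total, so 30 per arm before losses; 25 per arm stated as needed; primary outcome change from baseline; five visits including baseline.

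**Inputs assumed.** The documents do not give the correlation r between baseline and week-8 scores; I use 0.3 to 0.7. They do not give the effect size either; I use 0.5 and 0.79 SD of change.

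**1. The plan's own figure.** The Sample Size section says "it was determined that 25 participants would be needed in each treatment group to detect a difference with an overall 5% type-I error risk", but gives no effect size, SD or power, so 25 cannot be reproduced. Solved backwards for 80% power: d = (1.960 + 0.842) × √(2/25) = 0.79. This is the source of the 0.79 used below; it is not a figure the plan states.

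**2. How often chance would trigger adjustment.** If k independent baseline tests were run at 0.05, P(at least one positive) = 1 − 0.95^k. For k = 5, 10 and 20 this is 23%, 40% and 64%. Both k and independence are assumptions; correlated scales would lower these figures.

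**3. Precision at week 8.** With equal variance s² at both times, the change score has variance 2(1 − r)s² per person and the baseline-adjusted value (1 − r²)s². The ratio is (1 + r)/2.

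**4. Precision for the treatment-by-time slope.** Take five equally spaced visits, compound symmetry, linear time and complete data. Forcing a common baseline mean, instead of letting the arms differ at baseline, multiplies the variance of the slope difference by 1 − 0.4(1 − r)/(0.6 + 0.4r). At r = 0.5 this is 1 − 0.2/0.8 = 0.75. With time as a categorical factor, the week-8 contrast gives (1 + r)/2 again.

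**5. Power at 30 per arm.** The noncentrality is d√(30/2), divided by √((1 + r)/2) after adjustment. At r = 0.5 it goes from 1.94 to 2.24 for d = 0.5, and from 3.06 to 3.53 for d = 0.79. From the t distribution:

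| r | Variance ratio, week 8 | Variance ratio, slope | Power, 0.5 SD | Power, 0.79 SD |
|---|---|---|---|---|
| Unadjusted change | 1 | 1 | 48% | 85% |
| 0.3 | 0.65 | 0.61 | 66% | 96% |
| 0.5 | 0.75 | 0.75 | 59% | 93% |
| 0.7 | 0.85 | 0.86 | 54% | 90% |

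The power columns refer to the week-8 change contrast.

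**6. Test-then-adjust, by simulation.** With 20 independent baseline variables, adjustment for those below 0.05, d = 0.79, 30 per arm and 6,000 runs per cell, power for unadjusted change / test-then-adjust / prespecified adjustment was 86/84/96% at r = 0.3, 85/83/93% at r = 0.5 and 86/83/90% at r = 0.7. The type I error of test-then-adjust was 4.0% to 5.4% across 25 and 30 per arm. Only baseline Zanarini was prognostic in this simulation.

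**The case against.** The best defence has four parts.

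**No significance rule is written.** This stands. A reader might infer that covariates are selected at p < 0.05, because the tests come just before the adjustment sentence. The text gives no threshold, and a difference could be judged by size or clinical relevance. Likewise, it is only from sentence order that the comparison with pre-treatment drop-outs might also feed the adjustment. The plan is unspecified, not explicitly driven by significance.

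**No false-positive inflation.** This stands for a rule applied mechanically, as step 6 shows. Simulated freedom to report the better of an unadjusted and a baseline-adjusted analysis gave 7.5%, 7.2% and 6.6% at r = 0.3, 0.5 and 0.7 (30 per arm). That shows why an open model is undesirable, but nothing in the plan says the analyst would choose that way.

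**Baseline is already used.** This stands in part. A reader might infer that a baseline Zanarini imbalance goes uncorrected. It does not: change from baseline subtracts the baseline score in full, and the score could still enter as a covariate if it differed. What is lost is efficiency, because full subtraction is not the best weight when r is below 1.

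**The plan is a longitudinal model, not a two-point change score.** Adding baseline only as a main effect left the treatment-by-time estimate and its standard error unchanged in a test fit, so that remedy would not help an interaction test. A linear-slope model also recovers much of the gap between change score and baseline adjustment; at r = 0.5 the simulated variances of the 8-week difference were 0.052 for the slope model, 0.065 for the change score and 0.050 for baseline adjustment. The like-for-like comparison, however, is the slope model with and without a common baseline mean, and step 4 shows that the gain remains there.

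**Conclusion.** The point holds as one of prespecification and efficiency. The plan does not fix the covariates of its primary model, its natural reading lets chance imbalance choose them, and it does not prespecify adjustment for a baseline score that it always collects. Prespecified adjustment would lower the variance of the primary contrast by about 35% to 15% for r from 0.3 to 0.7. At 30 per arm and r = 0.5, that is 11 points of power at 0.5 SD (48% to 59%) or 8 points at 0.79 SD (85% to 93%). The gain shrinks as r rises.

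These sizes rest on assumed r and effect size, complete data, and either a week-8 change contrast or a common-baseline-mean model. The slope figures also assume compound symmetry and linear time. The 64% chance of triggered adjustment should not be quoted as a property of this trial, since it needs 20 independent tests that the plan does not list. The documents do not support a claim that the planned analysis is biased or invalid.

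**What to change.** In the Data Analysis section:

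- Delete the sentence that adjusts outcome analyses for observed baseline differences. Report baseline values descriptively by arm in place of the t-tests and chi-square tests.
- Prespecify one of two primary models. (a) Keep baseline Zanarini in the response vector, with a common baseline mean across arms. (b) Use post-baseline visits only as response, with baseline Zanarini and baseline-by-visit as fixed covariates. Under (b) the baseline value must not also be a response.
- Name any further covariates now, or state that there are none.
- Name the primary contrast, for example the week-8 treatment difference, and how time is coded.
- Treat each secondary scale the same way, with its own baseline.

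The cost is a few sentences before unblinding. No extra data, visits or participants are needed.

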Those subjects who appear appropriate for the study, based on telephone screening, will be invited for a baseline assessment. The duration of the baseline assessment will be approximately 90-120 minutes and will include the following: Informed consent, Demographic data, Concomitant medications, Family history data, Medical evaluation including physical examination, labs, EKG, weight, and vital signs, Urine pregnancy test (for women of childbearing years) and urine drug screen, and a psychiatric evaluation (using the following measures: MINI International Neuropsychiatric Interview (26); Depressive symptoms will be rated with the 24-item Hamilton Depression Rating Scale (HAM-D) (27); Anxiety symptoms will be assessed using the Hamilton Anxiety Rating Scale (HAM-A) (28); Psychosocial functioning will be evaluated using the patient-rated version of the Sheehan Disability Scale (SDS) (29); Quality of Life Inventory (QOLI) (30); The Cambridge-Chicago Compulsivity Trait Scale (CHI-T); and the Columbia Suicide Severity Rating Scale (C-SSRS), Minnesota Impulse Disorders Interview (MIDI), Dietary Fat and Free Sugar Questionnaire, Sensory Gating

Inventory). During the consent process, individuals will be given time to review the consent form and given the opportunity to ask any questions that may arise before signing the informed consent form. Throughout the study, subjects will be asked questions about the study to ensure that they continue understanding study procedures. Blood samples will be collected at both baseline and last visits to measure fasting total cholesterol, high-density lipoprotein cholesterol, low-density lipoprotein cholesterol, glucose, insulin, triglycerides, prolactin levels, liver function, and kidney function. All follow-up visits will include safety measures (adverse events, vital signs, C-SSRS), weight, BPD measures, and other psychiatric measures.

Efficacy evaluation

The primary outcome measure will be the change from baseline using the Zanarini Rating Scale for Borderline Personality Disorder (“Zanarini scale”) (31). This semistructured interview has anchored ratings (0=no symptoms, 4=severe symptoms) on nine items that correspond to the DSM-5 BPD criteria. Its subscales will be considered secondary efficacy measures.

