If a subject withdraws from the study, all instruments administered at the screening visit will be completed at the final visit. These will be conducted when the subject is able to come in for an early termination visit. Withdrawn subjects will be given the phone number of the principal investigator as well as the phone numbers of local resources for BPD treatment.

Subject Termination

If a subject fails to take the medication for a consecutive three-day period, they will be terminated from the study. In this case, the procedures for Subject Withdrawal will be followed (see above). Medication compliance will be assessed via pill count and subject report.

Safety Assessments

Safety and tolerability will be assessed using spontaneously reported adverse events data, C-SSRS, vital signs, and by evaluating premature termination. Safety assessments (sitting blood pressure, heart rate, adverse effects, concomitant medications, and motor tolerability using the Abnormal Involuntary Movement Scale) will be documented at each visit. Subjects who are an immediate suicide risk will be removed from the study and appropriate clinical intervention (e.g. hospitalization) will be arranged. Study team members are mandated reporters and as such, will arrange for the subject to be taken to the emergency room if any intent to harm themselves is expressed. Urine pregnancy tests will be performed at the initial visit. Subjects who have a positive urine pregnancy test will be excluded from the study. Assessment of side effects will be done at each visit.

Adverse Event Reporting

Unanticipated (unexpected) problems/events, those that are *not* already described as potential risks in the consent form, or *not* part of an underlying disease, will be reported to the IRB as soon as possible. The same will be done for serious problems/events and, in the opinion of the investigator, are possibly, probably or definitely related to the research procedures. A follow-up report will also be submitted to the IRB with any documentation related to a previously submitted adverse event.

Risks

While taking the study drug, the subjects condition may remain the same or worsen due to no effect of the study drug.

The most commonly reported side effects (greater than 2%) in previous clinical trials associated with Caplyta include:

24% of subjects experience:

- Somnolence/Sedation (Sleepiness)

14% of subjects experience:

- Headache

6-10% of subjects experience:

- Nausea
- Dry Mouth

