- Extrapyrimal symptoms (which may include muscle spasms, stiffness, restlessness, tremor, and drooling, and may be irreversible)

- Increased total cholesterol and triglycerides

3-5% of subjects experience:

- Dizziness
- Creatine Phosphokinase Increased (abnormal liver function tests)
- Fatigue
- Vomiting
- Diarrhea
- Blurred vision
- Hyperglycemia (increased blood sugar levels)

2% of subjects experience:

- Hepatic Transaminases Increased (abnormal liver function tests)
- Decreased appetite
- Abdominal pain
- Upper respiratory tract infection
- Increased blood prolactin

The following side effects have been experienced by some people who have used Caplyta outside of clinical trials. Because these reactions are reported voluntarily from a population of uncertain size, it is not always possible to reliably estimate how common these side effects are, or if they are related to the study drug. **These reactions may be severe, life-threatening, or fatal, and include:**

These reactions may be severe, life-threatening, or fatal, and include:

- Dystonia (abnormal contractions of muscles, may cause difficulty breathing)
- Leukopenia (low white blood cell count)
- Neutropenia (low amount of neutrophils in the blood)

The following side effects have been experienced by people who have taken antipsychotics, which is the class of medication that Caplyta belongs to. **These reactions may be severe, life-threatening, or fatal, and include: These reactions may be severe, life-threatening, or fatal, and include:**

- Suicidal thoughts and behaviors
- Increased risk of death in elderly people with dementia related psychosis
- Stroke in elderly people with dementia-related psychosis that can lead to death
- Weight gain
- Orthostatic hypotension (low blood pressure that occurs upon standing)
- Syncope (fainting)
- Falls
- Seizures
- Body temperature dysregulation
- Dysphagia (difficulty swallowing)

It is possible that some of the questions we will ask you about BPD symptoms or mood might make the subject uncomfortable. They can decline to answer any questions that make them feel uncomfortable.

There may be other risks that could arise which are not reasonably foreseeable. If new information becomes available which could influence your willingness to continue, this new information will be discussed with the subject.

Data Analysis

Data analysis will involve all visits during the 8-week double-blind treatment phase (up until week 8).

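### The efficacy set is chosen after randomisation and the mixed model has no stated baseline Zanarini adjustment, so early loss that depends on baseline severity and differs by arm could bias the primary contrast.

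*Combined protocol and SAP*

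**What the plan says.** All references are to the combined protocol and SAP.

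- **Analysis sets (Data Analysis).** Intent-to-treat is attached to demographics and safety: "All enrolled subjects will be included in the analyses of baseline demographics and safety according to an intent-to-treat (ITT) principle". The full-analysis set, to be used for statistical analysis, is "all participants who took at least 1 dose of the study drug and had at least 1 post-baseline primary efficacy assessment". The section does not literally call this the primary efficacy set, but no other efficacy set is defined, and no sensitivity analysis is planned.
- **Endpoint (Efficacy evaluation).** "The primary outcome measure will be the change from baseline using the Zanarini Rating Scale for Borderline Personality Disorder".
- **Model (Data Analysis).** A linear mixed-effects model that "includes terms for treatment group, time, and treatment-by-time interaction". On the data used: "Data analysis will involve all visits during the 8-week double-blind treatment phase (up until week 8"). On missing values: "so no imputation will be undertaken for missing data". The text does not say whether the baseline score is a response at time zero or is subtracted to form change scores.
- **Baseline adjustment (Data Analysis).** After describing baseline comparisons, the section says that outcome analyses will be adjusted for baseline differences by covariance methods. It names no covariate.
- **Visits (Treatment Duration, Visit Frequency, and Procedures).** "Subjects will be seen at baseline and then every two weeks after that for a total of 5 visits", so the first scheduled follow-up is at week 2.
- **Withdrawal (Subject Withdrawal).** The screening instruments are repeated at a final visit: "These will be conducted when the subject is able to come in for an early termination visit".

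**The concern.** Taking a dose and having a post-baseline score are both events after randomisation. A set selected on them need not keep the balance that randomisation created. The plan itself provides routes to early loss: discontinuation for intolerance, termination after three consecutive days without medication, and removal for immediate suicide risk. The first could differ by arm and the last could relate to severity, although the documents give no rates for either.

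If one arm loses its more severe participants before any follow-up, the analysed arms differ at baseline. Severe participants also tend to show larger falls through regression to the mean. An analysis of change that does not adjust for baseline then credits part of that difference to treatment. Loss of severe participants from the active arm works against the drug, and the same loss from placebo works in its favour.

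**Working it through.** The plan gives no figure for early loss, Zanarini SD or correlation, so there is no stated result to reproduce. What follows is an illustration.

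**Inputs.** From the documents: 60 participants, 1:1, hence 30 per arm; baseline plus weeks 2, 4, 6 and 8; two-sided 0.05. Assumed: approximately normal scores with equal SD at baseline and week 8 (an approximation, since entry requires a score of at least 9); baseline to week-8 correlation r = 0.5, range 0.3 to 0.7; one arm loses its most severe fraction q before any follow-up and the other arm loses nobody.

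**Step 1. Baseline shift.** Removing the top fraction q lowers that arm's baseline mean by φ(z)/(1 − q) SD, where z is the (1 − q) quantile.

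**Step 2. Shift in the change-score contrast.** (1 − r) × the baseline shift.

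| q | z | Baseline shift (SD) | Contrast shift, r = 0.5 | r = 0.7 | r = 0.3 |
|---|---|---|---|---|---|
| 5% | 1.645 | 0.1031/0.95 = 0.109 | 0.054 | 0.033 | 0.076 |
| 10% (3 of 30) | 1.282 | 0.1755/0.90 = 0.195 | 0.097 | 0.058 | 0.136 |
| 15% | 1.036 | 0.2332/0.85 = 0.274 | 0.137 | 0.082 | 0.192 |

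For scale, 30 per arm detects about 0.74 SD by t-test at 80% power. The plan states no power, so 80% is also assumed. The r = 0.5 column is then about 7%, 13% and 19% of that difference (0.054, 0.097 and 0.137 divided by 0.736).

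**Step 3. Which change removes the bias.** A simulation used 30 per arm, five visits, SD 5, correlation 0.5, a true week-8 difference of −4 points, 3,000 runs and known covariance. The Monte Carlo error of each bias is about 1.35/√3000 = 0.025 points. Entries are bias in points.

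| No follow-up (placebo vs active) | Model | Current set | All randomised |
|---|---|---|---|
| 5% vs 15%, depends on baseline | Baseline as response, separate arm means | +0.41 | 0.00 |
| same | Unadjusted change score | +0.41 | +0.41 |
| same | Baseline as response, common mean | −0.01 | −0.01 |
| 5% vs 5%, depends on baseline | Separate arm means | −0.03 | −0.03 |
| 5% vs 15%, completely random | Separate arm means | 0.00 | 0.00 |
| 5% vs 15%, depends on the unseen week-2 score | Separate arm means | −0.03 | −0.23 |
| same | Common mean | −0.22 | −0.22 |

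The +0.41 is about 10% of the assumed effect (0.41/4). Three things follow. With separate arm means, keeping everyone randomised removes the bias. With change scores as the response, a person without follow-up adds nothing, so enlarging the set does nothing. With a common baseline mean, the constraint removes the bias and both sets give the same estimate.

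**Step 4. Precision.** With complete data at r = 0.5, the contrast's standard error is √(2 × 2(1 − r)/30) = 0.258 SD for change scores and √(2(1 − r²)/30) = 0.224 SD with the common mean, about 13% smaller. With loss as in the 10% case, the values are about 0.26 and 0.23 SD.

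**The case against.** **The plan already adjusts for baseline.** If the covariance sentence covers the baseline Zanarini score, the illustrated bias largely disappears in the existing set. This is the strongest objection, and it stands as a possibility. But the sentence names no covariate and the model statement lists none. If adjustment is triggered by a significant baseline test, it would usually not happen. A 0.195 SD difference with 30 against 27 has standard error √(1/30 + 1/27) = 0.265 SD, so noncentrality 0.735 and about an 11% chance of detection.

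**Few will be excluded.** The Sample Size section expects few drop-outs, and the early-termination visit may supply a post-baseline score for some who leave before week 2. Both points stand. No rate is given, however, the visit depends on attendance, and three people are 10% of an arm.

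**The set hardly matters once the model is right.** This is correct. A reader might infer that keeping participants with only a baseline score is what removes the bias. That holds only with separate arm means and baseline as a response, which the plan permits but does not state.

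**The worst case is not evidence.** This is also correct. A reader might take the 24% somnolence/sedation figure under Risks as a sign of early loss in the active arm. It is the frequency of an adverse event, with no placebo figure beside it, and says nothing about discontinuation.

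**The fix can do worse.** In the scenario where loss depends on the unseen week-2 score, the common-mean model was biased by −0.22 points against −0.03 for the current set with separate means. No general ranking follows from one scenario, but it shows that the fix does not cure non-random loss.

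**Conclusion.** The point holds as a gap in specification with a possible, modest bias. The efficacy set depends on post-randomisation events, no all-randomised efficacy analysis is planned, and the role of the baseline score is unstated. The worst-case bias is about 0.05 to 0.14 SD for loss of the most severe 5% to 15% in one arm only, at an assumed correlation of 0.5. It requires all three of: loss related to baseline severity, a different pattern of loss between arms, and a model with separate baseline means or unadjusted change scores. Without any one of these it is about zero.

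A reader might go further and conclude that the planned primary result will be biased, or that everyone who misses week 2 is dropped. The documents support neither. A later visit or an early-termination score keeps a person in the set, and the model may yet be fitted with baseline adjustment. The change is still worth making, because it is cheap and also improves precision.

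**What to change.** In the Data Analysis section, before unblinding:

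1. Define the primary efficacy set as all randomised participants with a baseline Zanarini score, analysed in the arm to which they were randomised.
2. State that the baseline score is a response at time zero and that the two arms share one baseline mean, so treatment differences enter only at post-baseline visits. A prespecified baseline Zanarini covariate serves the same purpose for this bias, although participants with only a baseline score then drop out of the fit.
3. Say that this baseline handling applies whatever the baseline tests show.
4. Add a sensitivity analysis for loss that depends on unseen scores, for example by shifting the assumed outcomes of early leavers by arm over a stated range. Re-running the current set would add little, because under the common-mean model it gives almost the same estimate.
5. Report by arm the number of participants with no post-baseline score.

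The cost is a few sentences, a small change to the model code and one added sensitivity analysis. No new data are needed.
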